This IRB application addresses the second of three aims for our overall research plan: to evaluate a mobile-phone delivered medication adherence intervention (called REACH; Rapid Education/Encouragement And Communications for Health) and test intervention effects on adherence and glycemic control among low income adults with type 2 diabetes mellitus (T2DM) receiving primary care at Federally Qualified Health Centers (FQHCs) or VUMC. In addition, family-focused components (called FAMS; Family-focused Add-on to Motivate Self-care) are integrated with the larger REACH intervention, and include diabetes coaching, goal-focused text messages delivered to the patient, and supplemental text messages delivered to an identified adult family member. We will evaluate the effects of the supplemental, family-focused intervention on family members' supportive and obstructive behaviors, patients' diabetes self-efficacy, and patients' adherence to diet and exercise. (Aim 1, to improve the content and functionality of an existing mobile phone-delivered medication adherence promotion intervention for consistency with the Information-Motivation-Behavioral skills model and clear health communication strategies, and test for usability and acceptability with patients, received approval [see IRB #140562] in April 2014.)

Expected duration of the study.

We expect to complete data collection by the end of 2019, but the study will remain open for analyses and manuscript writing/submissions for an additional five years.

The IRB needs to understand how this study adds to the knowledge on this topic in order to be able to judge the risks and benefits to the research participants.

BACKGROUND

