Neighborhood Health participants sign an R01 as part of clinic processes. Once signed, the hard copy of the document will be scanned for the clinic to store in their EMR. We will store a scanned copy on our secure VUMC shared drive until the end of the study. We will store hard copies with the date of birth and Social Security Number (an optional field for the participant to fill out) redacted in our locked file cabinet separate from study data until the end of the study.

Describe how the confidentiality of participants' data will be assured. Include a description of any issues specific to the study that might increase the risk of breach of confidentiality. Describe how codes will be generated if codes are used to protect identities, and who will have access to such codes. If a certificate of confidentiality will be provided, include the name of the person holding the certificate. Describe the final disposition of research data when the study is concluded (e.g., will information be destroyed, will the PI maintain the information indefinitely, etc.).

KSP will assign participants a unique subject ID associated with their identifiable information in REDCap. Family member participant information is linked to the patient participant. All transcripts, surveys, message response data, and audio-recordings will be de-identified. KSP will use REDCap to record and electronically store survey data. REDCap is developed specifically around HIPAA security guidelines and is a secure, web-based application housed in a local data center at Vanderbilt. All de-identified data will be stored in password-protected files and retained on a secure VUMC server for at least ten years after the close of the study.

RANDOMIZATION - Describe the randomization process (who will randomize, how will randomization be determined, etc.)

After completing informed consent and enrolling in the study, participants are randomized to one of three study groups: REACH, FAMS, or control (see Research Study Design). Randomization is determined with a statistical script developed in R, and run by a member of KSP. (This feature is not yet integrated into REDCap. Once available, this will occur in REDCap). Unblinded KSP calls each participant prior to the Sunday in which they will begin the program to communicate what they can expect based on their study group assignment (see REACH, FAMS, and Control Condition Explanations).

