**REACH Intervention:
Improving Medication Adherence Among Underserved Patients With Type 2 Diabetes**

NCT02409329

03/31/2020

NCT02409329 – Statistical Analysis plan

REACH treatment effects – any REACH vs. Control

All analyses were performed using R v.3.5.1. We employed multiple imputation with chained equations to address missing data ($m=1,000$ imputed datasets). Statistical significance for each hypothesis test was determined at the $\alpha=0.05$ level. All analyses compare those receiving the REACH intervention (i.e., REACH or REACH + FAMS) to control except for the subgroup analyses estimating additional effects of also receiving FAMS.

We used generalized estimating equations (GEE) with a working-exchangeable correlation structure and identity link (1), adjusting for baseline and allowing a time-treatment interaction. We adjusted for the baseline value of the outcome of interest with restricted cubic splines (three knots) to allow for a nonlinear effect of the baseline value. For each outcome, we performed an omnibus test of the treatment effect using a robust variance-covariance based Wald statistic. We used ordinary least squares linear regression with Huber-White heteroscedasticity-consistent standard errors (2) to obtain point estimates and 95% CIs for the intervention effect on each outcome at each time point.

REACH only and REACH+FAMS vs. Control

Half of the intervention group received REACH only and the other half received REACH+FAMS for the first 6 months. Both intervention groups received REACH only during months 6-12. Data visualizations suggested effect modification by baseline HbA1c, in which those with a higher baseline HbA1c demonstrate a larger estimated effect at 3 and 6 months than those with a lower baseline HbA1c. To increase our power to detect any differential effects for REACH only as compared to REACH+FAMS, we conducted analyses with a subset of data including participants with a baseline HbA1c $\geq 8.5\%$ (69 mmol/mol; $n=219$), which was the approximate mean value for baseline HbA1c. With this reduced dataset, we conducted the same GEE model described above for REACH only vs. control and, separately for REACH+FAMS vs. control. We used ordinary least squares linear regression with Huber-White heteroscedasticity-consistent standard errors (2) to obtain point estimates and 95% CIs for the intervention effect on each outcome at each time point.

References:

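### The SAP's subgroup section asks what FAMS adds to REACH only, but specifies only two separate models against control, so that difference has no SE, CI or test.

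*SAP*

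**What the plan says.** The SAP states the FAMS question twice. Under *REACH treatment effects – any REACH vs. Control*, it sets the default comparison and an exception: "All analyses compare those receiving the REACH intervention (i.e., REACH or REACH + FAMS) to control except for the subgroup analyses". It describes those as "subgroup analyses estimating additional effects of also receiving FAMS". Under *REACH only and REACH+FAMS vs. Control*, it explains why the analysis was restricted to participants with baseline HbA1c of at least 8.5% (n=219): "To increase our power to detect any differential effects for REACH only as compared to REACH+FAMS".

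The models then specified are different. The analysts "conducted the same GEE model described above for REACH only vs. control and, separately for REACH+FAMS vs. control". OLS regressions with heteroscedasticity-consistent standard errors follow, giving estimates and 95% CIs for an intervention effect at each time point. The same phrase in the main section means the effect against control.

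On design, the protocol's randomization section says "participants are randomized to one of three study groups: REACH, FAMS, or control". The SAP adds "Half of the intervention group received REACH only and the other half received REACH+FAMS for the first 6 months". It does not give arm sizes in the subset or the allocation ratio to control.

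**The concern.** Both statements of the question describe a difference between the two active arms. Both models describe a difference from control. The subset was therefore justified by power for a comparison that is never specified.

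The two control comparisons do not answer the question by themselves. Their difference estimates the FAMS increment, approximately because the baseline spline is fitted separately in each model. Its exact SE needs the covariance that arises from the shared control patients. An approximation from arm sizes under equal variances is possible, but the SAP does not give those sizes. A significant result in one model beside a non-significant result in the other is not a test of the difference.

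The stake is any statement about what FAMS adds. Patients were randomised to three groups, so a direct randomised comparison is available.

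**Working it through.** There is no stated power, SD or effect size for this contrast, so there is no plan figure to reproduce. The first step is a reading of the text; the rest is illustration.

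**Text check.** Question: REACH+FAMS against REACH only, stated twice in the SAP. Models: REACH only against control, and REACH+FAMS against control. Neither document gives a three-arm model, a between-arm contrast, or an SE, CI or test for one.

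**Inputs.** From the SAP: n = 219, alpha = 0.05, equal halves of the intervention group. Assumed: two-sided test, unit SD, equal variances, no gain from covariates, no missing data, equal active arms within the subset, and control share of 1/3 (1:1:1) or 1/2 (2:1:1, control first). This gives 73 per arm, or 109.5 control and 54.75 per active arm. Write n for an active arm and nc for control.

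**Standard errors (SD units)**
- Each arm against control, sqrt(1/n + 1/nc): 0.1655 in both cases.
- Direct contrast, sqrt(2/n): sqrt(2/73) = 0.1655; sqrt(2/54.75) = 0.1911.
- Difference of the two control comparisons if treated as independent, sqrt(2(1/n + 1/nc)): 0.2341 in both cases.
- Ratio: 0.2341/0.1655 = 1.414 (41% too large); 0.2341/0.1911 = 1.225 (22% too large).
- Correlation of the two control comparisons, (1/nc)/(1/n + 1/nc): 0.50; 0.33.

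**Power if FAMS truly adds 0.3 SD**
- Direct contrast: 44% (1:1:1), 35% (2:1:1).
- Independence shortcut. The critical difference is 1.96 × 0.2341 = 0.459, while the true sampling SE stays 0.1655 or 0.1911. Then (0.3 − 0.459)/0.1655 = −0.96 gives 17%, and (0.3 − 0.459)/0.1911 = −0.83 gives 20%.

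**Discordant verdicts when FAMS adds nothing.** The table gives the probability that exactly one arm is significant against control, both arms having the same true effect (bivariate normal with the correlations above):

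| Power of each comparison | 1:1:1 | 2:1:1 |
|---|---|---|
| 30% | 28.7% | 33.5% |
| 50% | 33.3% | 39.2% |
| 80% | 22.6% | 26.1% |

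A direct test rejects in 5%. Simulation agrees.

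**Precision of the direct contrast in n = 219**
- Difference detectable with 80% power, (1.960 + 0.842) × SE: 0.464 SD; 0.535 SD.
- 95% CI half-width, 1.96 × SE: 0.324 SD; 0.375 SD.

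**The case against.** The strongest reply is that this is a wording mismatch in a secondary, exploratory section. The heading says each arm against control, and the models match it. The subset was prompted by the data ("Data visualizations suggested effect modification by baseline HbA1c"), and the SAP is written in the past tense. Dropping two phrases would restore consistency. This stands as far as it goes, and dropping them is one of the two remedies below. It does not remove the gap while the phrases remain: an exploratory question still needs an estimate with its uncertainty.

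The protocol's support is also limited. Its opening paragraph says "We will evaluate the effects of the supplemental, family-focused intervention on family members", then goes on to those family members' supportive and obstructive behaviours, and to patients' self-efficacy, diet and exercise. It names no comparator and does not mention HbA1c there. That is fair: the sentence is background, and the point rests on the SAP.

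Third, the SE inflation and the discordance rates price mistakes that the SAP does not propose. The independence shortcut is even conservative, since it overstates the SE. This also stands: the figures show what can happen when no contrast is given, not what the analysts did.

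Last, a direct contrast in n = 219 is weak, and using all randomised patients would be more precise. If the protocol's accrual goal of 525 were all patients (an assumption; it may include family members), the detectable difference would be 2.802 × sqrt(2/175) = 0.30 SD (1:1:1) or 2.802 × sqrt(2/131.25) = 0.35 SD (2:1:1). That is a reason to report the wider contrast as well. In the subset, a wide CI shows the imprecision openly, and the comparison is still randomised because the subset is defined by a baseline value.

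**Conclusion.** The concern holds. Followed exactly, the subgroup section yields no SE, CI or test for the difference that it says it set out to detect. This should be fixed, but it does not touch the main analysis of any REACH against control.

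The gap itself follows from the SAP's text and needs no assumption. Its illustrated size depends on the assumed allocation, equal variances and a two-sided test. It also depends on a reader either combining the two control comparisons as if independent or comparing their significance. The SAP proposes neither.

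**What to change.** Fit one model with a three-level arm factor (control, REACH only, REACH+FAMS), arm by time and the baseline spline, pooled over the imputed datasets. The SAP's OLS regression at each time point, with the same three-level factor, would also serve. In the n = 219 subset, report REACH+FAMS minus REACH only with robust SE, 95% CI and p-value at 3 and 6 months, the assessments within the period when FAMS was delivered. Label the contrast a post hoc addition and state the arm sizes. Base any statement about FAMS's added effect on it. Reporting the same contrast in all randomised patients is a useful option.

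The alternative is to delete the additional-effects and differential-effects wording and say that each arm was compared with control only.

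The cost is SAP wording and two contrasts per outcome (3 and 6 months) from data already held. The contrast will be imprecise in the subset, and a post hoc contrast carries less weight than a prespecified one. Both should be said in the report.
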